3.2. Inclusion and Exclusion Criteria

a) Inclusion Criteria:

- a. Adults aged 18 and older
- b. Clinical diagnosis of Ménière's disease, with classical symptoms:
 - i. Episodic spinning vertigo
 - ii. Fluctuating unilateral low frequency sensorineural hearing loss
 - iii. Tinnitus
 - iv. Aural fullness
- c. Failure of traditional medical management of Ménière's disease symptoms
- d. English language skills sufficient to provide informed consent to the study

b) Exclusion Criteria:

- a. Atypical medical history of Ménière's symptoms and questionable Ménière's diagnosis
- b. Bilateral Ménière's disease

3.3. Discussion of Subject Population

These patients will have already received the standard medical regimen for idiopathic Ménière's disease of diuretics, vestibular sedatives and a low salt/low caffeine diet, but this traditional medical treatment for Ménière's disease will not have resolved their disease symptoms. They will have completed a thorough pre-surgical workup and would normally be offered surgical interventions that would include the endolymphatic-mastoid shunt/decompression, transtympanic Dexamethasone, transtympanic chemical/gentamicin labyrinthectomy or a vestibular nerve section. Subjects entering the study will be offered a non-surgical, experimental and alternative form of treatment, and will be randomized into either the control/placebo arm or treatment arm of the study.

4. SUBJECT IDENTIFICATION, RECRUITMENT AND CONSENT

4.1. Method Of Subject Identification And Recruitment

Patients will be recruited from the clinical practice of the principal investigator.

4.2. Process of Consent

If eligible, patients will be approached by the PI to discuss the study. Candidate subjects will be assured that their decision to participate or not to participate will not affect the medical care that they can expect. If they are interested in participation, they may take the consent form home or they may provide consent at that time. When ready to consent, the teach-back method will be used to ensure that the subject understands their participation in the study. Preferentially, consent will be obtained by study personnel other than the PI, however due to logistics this may not be possible or convenient to the subject, in which case the PI may obtain consent.

Consent will be documented in a consent log in REDCap and signed forms will be stored in the Otolaryngology Department Research Office (SMH 1.5010). The subject will receive a copy of the signed form.

5. METHODS AND STUDY PROCEDURES

The screening visit may take place up to 30 days prior to the first study visit, or may occur on the same day as the first study visit. After providing informed consent, subjects will provide a complete medical and neuro-otological history/exam and the study team would review their standard of care Ménière's work-up. Because subjects are typically established patients of the PI, the history may be obtained retrospectively from the subject's chart.

At the screening visit and at each subsequent visit, the subject will complete the ‘Meniere’s functional level scale’ question (Appendix B).

At the first study visit (which might be the same day as the screening visit) the study team will confirm eligibility and the subject will be randomized to either the oscillation or placebo group, with the study team blinded as to which treatment is received. The study team will be informed whether Device A or Device B are to be used (see 7.2). For treatment, the subject will be in a private room at the Department of Otolaryngology Clinton Woods Clinic. The designated treatment device (oscillator or placebo) will be placed over the mastoid of their involved ear and secured via an elastic/Velcro headband. The subject is positioned so as to place the endolymphatic duct into a gravitationally dependent orientation (the subject lying on their contralateral side with the face slightly tilted towards the floor). The device is turned on and operated for 30 minutes. The subject will be periodically monitored by study staff during this time. Following each treatment, patients will be evaluated for response and untoward side effects.

Study visits 2, 3 and 4 will be 7 days apart. Prior to treatment, a thorough review of the behavior of the subject’s Ménière's disease over the preceding week as well as any sequelae of their treatment will be recorded. A complete ENT and neuro-otologic exam will be completed.

Study visit 5 will be two weeks following the final treatment visit (visit 4). Subjects will have a complete medical and neuro-otologic exam and be observed for short-term results of the treatments.

The final study visit will be three months after study enrollment. Subjects will have a complete medical and neuro-otologic exam and be observed for longer-term results of the treatments. Specifically, the frequency and severity of any Ménière's disease attacks will be recorded and compared to pretreatment patterns.

Schedule of Activities

Visit	0 (Screening)	1	2	3	4	5	6 (Final)
Visit Window	-30 days	0 days	7 days	14 days	21 days	35 days	90 days
Obtain informed consent	X	(X)					
Medical and otologic history	X	(X)					
ENT and neuro-otologic exam	X	(X)	X	X	X	X	X
Confirm eligibility/Randomize		X					
Document any recent vertigo		X	X	X	X	X	X
Meniere’s functional level scale (Appendix B)		X	X	X	X	X	X
Mastoid Oscillation/Placebo		X	X	X	X		
Document acute response		X	X	X	X		
Adverse event review		X	X	X	X	X	X

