5.2. Safety Assessments

As standard of care for evaluation and management of any Ménière's disease patient who has failed medical treatment and who is considering alternative forms of treatment, patients will provide information on their general medical and specific otologic health. They typically receive a thorough ENT and neuro-otologic physical exam per SOC. SOC audiologic testing is conducted if no previous testing in the 3 months prior to their visit is available. SOC ENG/VNG testing is not always necessary in the workup of the patient with Ménière's disease, but might be completed on a case by case basis per SOC. An MRI/MRA scan of the head would be completed on all patients per SOC to assure that there are no incidental tumors or aneurysms. Appropriate SOC screening lab tests would be completed to rule out metabolic, endocrine, inflammatory and autoimmune issues.

For safety assessment, the initial standard of care Ménière's workup described above will be documented when the subject enters the study. At each study visit after the first, subjects will be asked about changes to medical and otologic health, and in particular if they have had vertigo episodes since the last visit, and if so how frequent and of what duration. We will also ask if they experienced any discomfort related to the treatment and the subject will complete the 'Meniere's functional level scale' question (Appendix B).

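### The study team is told each subject's device letter and nothing keeps it from whoever records vertigo, so if letters are fixed to arms one clue could unblind later primary-outcome records

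*Combined protocol and SAP*

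**What the plan says.** - **Blinding and the letter.** Section 5 has subjects randomised at the first study visit "with the study team blinded as to which treatment is received". The next sentence reads "The study team will be informed whether Device A or Device B are to be used". No team member is excepted.
- **Where the letter comes from.** Under section 7.2 the department chair keeps the allocation table secret and releases one of two device letters per subject, in a 1:1 ratio. Whether a letter stands for the same arm throughout is not stated.
- **The devices.** Sections 2.2 and 7.1 say that the placebo device matches the sound but delivers no vibration. Section 7.1 adds that vibration or sound starts a few seconds after switch-on.
- **Contact during treatment.** The device runs for 30 minutes at each of four visits (section 5). "The subject will be periodically monitored by study staff during this time". "Following each treatment, patients will be evaluated for response and untoward side effects".
- **Recording of vertigo.** The Schedule of Activities lists "Document any recent vertigo" at visits 1 to 6. At visits 2 to 4 the review before treatment covers the past week's disease, and the same sentence ends "as well as any sequelae of their treatment will be recorded". Section 5.2 has subjects asked, at each visit after the first, "in particular if they have had vertigo episodes since the last visit, and if so how frequent and of what duration". It then adds: "We will also ask if they experienced any discomfort related to the treatment". No role is named for any of this.
- **Primary outcome.** Section 11.2 uses X/Y × 100, the monthly rate of definitive spells after therapy (X) relative to the rate before it (Y). The blind is broken only after the last subject completes.

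**The concern.** Coded labels are ordinary masking, and someone has to know which device to fit. The difficulty is that section 5 spreads the label more widely than fitting requires. If one letter is one arm, everyone who holds the letters is one clue away from knowing the allocation of many subjects, not just the subject who gave the clue.

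The primary outcome is built from what subjects tell staff. If the person taking that history has worked out the letter, questioning or counting could differ by arm. This trial was designed to answer the objection that the pilot lacked controls, so an avoidable doubt about the blinding of its main outcome weakens the answer it is meant to give.

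**Working it through.** The plan gives no figure on this point to reproduce. The check is a reading of the sections side by side, with two counts.

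**1. Who holds the letter, and who needs it.** Section 5 gives it to the study team without qualification. Only the person who fits and runs the device needs it. No section withholds it from the person who records vertigo, and that person is not named. Section 8.2 allows otolaryngologists to give the treatment, so operator and examiner could be the same person, but nothing says that they are.

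**2. What a clue would decode.** The letter alone reveals nothing. A clue is also needed, such as vibration felt by staff or a remark by a subject. With two letters and two devices, the natural inference is that one clue fixes both letters. If the mapping is not fixed, the clue reaches only the subject concerned.

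**3. Opportunity for a clue.** 15 active subjects × 4 sessions = 60 sessions. 60 × 0.5 h = 30 h with a vibrating device running and staff looking in. The documents give no chance of a clue per session, so this count is not turned into a probability.

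**4. What each safeguard covers.**

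| Safeguard | Protects | Keeps the letter from the recorder? |
|---|---|---|
| Secret table (7.2) | The key | No |
| Matched sound (2.2, 7.1) | Audible clues | No |
| Delayed start (7.1) | First few seconds of a 30-minute session | No |
| Late unblinding (11.2) | Formal disclosure | No |
| No device in use at visits 5 and 6 (Schedule) | New clues on those days | No; a letter decoded earlier is still known |

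**5. Which records feed X.** The documents do not fix the window for X. If it is assumed to run from the last treatment (day 21) to the final visit (day 90), the review before treatment at visit 4 already falls at its start, and only visits 5 (day 35) and 6 (day 90) supply it: 2 visits × 30 subjects = 60 recordings. Vertigo recorded at visits 2 to 4 enters X only if the window starts earlier.

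**6. Which records are safe.** Anything recorded before the clue is unaffected. Y will mostly be safe, because section 5 lets the history come from screening or the chart, before the letter is released. The exception is a rate taken at visit 1 after randomisation; the order of steps within that visit is not given.

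**The case against.** The strongest reply is that this is an absent detail in a plan with several real safeguards, that a separate recorder may exist in practice, and that the letter is harmless without a clue. Much of that stands. The documents show no breach. The fixed mapping is an inference. Section 5.2 places the vertigo and discomfort questions at the same visit, not necessarily with the same person.

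It does not dispose of the point, because section 5 is not silent. It states a rule that gives the letter to the team, so the stated blinding depends on no clue ever reaching any member who records outcomes.

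A second reply is that spells are reported by the subject, who may feel vibration or its absence, so masking the recorder leaves a more direct route open. That is correct. It limits what the fix achieves but does not justify leaving the second route open as well.

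A third concerns cost. Section 4.2 admits that logistics may prevent someone other than the principal investigator from obtaining consent, so a second person at every treatment visit cannot be assumed. This also stands, and the fix is graded accordingly.

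A reader might infer that biased recording could by itself produce a positive trial. The documents do not support that. On the responder split of section 11.1, with 2/15 placebo responders, two-sided Fisher gives p = 0.021 at 9/15 active and p = 0.0078 at 10/15, so 10/15 is needed to meet the 0.012 used there. That is a large shift for recording alone. The reassurance is partial: section 11.2 states no alpha and compares classes A to F.

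**Conclusion.** The point holds as a gap in the masking that should be closed. If each letter denotes one arm throughout, one clue could reveal the arm of every subject whose vertigo is recorded after it. With a day 21 to 90 window, up to 60 recordings at visits 5 and 6 are exposed, fewer the later the clue comes. Both conditions are assumptions.

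A reader might go further and conclude that the trial is effectively unblinded, or that one clue compromises all 30 subjects. Neither follows. The first would need evidence of a clue, and there is none. The second is the worst case of a clue before any outcome is recorded. The direction and size of any bias cannot be estimated: the documents give neither the chance of a clue nor the discretion the recorder has over what counts as a spell.

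**What to change.** 1. In section 5, replace "The study team will be informed whether Device A or Device B are to be used" with: *Only the staff member who fits and runs the device is told the device label.*
2. Have subjects write down their spell counts before any staff contact at visits 2 to 6, and state that this written count is the source for X. The form should say what counts as a definitive spell, since section 11.2 counts only those.
3. At visits 5 and 6, have vertigo history taken by an existing team member who has not been told the label. Do the same at visits 2 to 4 where existing staffing allows.

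**Cost.** One changed sentence, a short form at five visits, and some scheduling of existing staff. Sections 4.2 and 7.1 show that the team includes the principal investigator, other study personnel and a research technician. The first two changes need no added staff. Devices, visits and sample size are unchanged.

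**What remains.** Subjects may still perceive vibration or its absence, and may mention it to the person taking the history.

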5.1. Efficacy Assessments

Efficacy will be determined by comparing the frequency and severity of post-treatment Ménière's disease attacks with pretreatment patterns. Clinical response will be classified by AAO guidelines⁴: frequency of definitive vertigo episodes per month, average hearing threshold, word recognition score, and functional level.

5.2. Safety Assessments

As standard of care for evaluation and management of any Ménière's disease patient who has failed medical treatment and who is considering alternative forms of treatment, patients will provide information on their general medical and specific otologic health. They typically receive a thorough ENT and neuro-otologic physical exam per SOC. SOC audiologic testing is conducted if no previous testing in the 3 months prior to their visit is available. SOC ENG/VNG testing is not always necessary in the workup of the patient with Ménière's disease, but might be completed on a case by case basis per SOC. An MRI/MRA scan of the head would be completed on all patients per SOC to assure that there are no incidental tumors or aneurysms. Appropriate SOC screening lab tests would be completed to rule out metabolic, endocrine, inflammatory and autoimmune issues.

For safety assessment, the initial standard of care Ménière's workup described above will be documented when the subject enters the study. At each study visit after the first, subjects will be asked about changes to medical and otologic health, and in particular if they have had vertigo episodes since the last visit, and if so how frequent and of what duration. We will also ask if they experienced any discomfort related to the treatment and the subject will complete the 'Meniere's functional level scale' question (Appendix B).

5.3. Costs to the Subject

There will be no cost for the actual treatment procedure or additional costs related to subjects' participation in this study. Study visits will not be billed to insurance. .

5.4. Payment for Participation

Subjects will not be paid for participating.

5.5. Return of Individual Research Results

Individual research results will not be provided back to subjects.

6. SUBJECT WITHDRAWALS

Subjects will be advised in the written informed consent forms that they have the right to withdraw from the study at any time without prejudice. Subjects will be withdrawn from the research without their consent by the investigator if they are non-compliant (miss scheduled study visits), or if the investigator determines that it is in the best interest of the subject. Also if the subject develops bilateral Ménière's disease during the study they will be withdrawn. There are no additional study activities requiring completion prior to subject withdrawal from the study. Subjects withdrawn from the study will not be replaced.

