9. CONFIDENTIALITY OF DATA AND INFORMATION STORAGE

Information about study subjects will be kept confidential and managed according to the requirements of the Health Insurance Portability and Accountability Act of 1996 (HIPAA). Those regulations require a signed subject authorization informing the subject of the following:

- What protected health information (PHI) will be collected from the subjects in this study
- Who will have access to that information and why
- Who will use or disclose that information
- The rights of a research subject to revoke their authorization for the use of their PHI

In the event that a subject revokes authorization to collect or use PHI, the investigator, by regulation, retains the ability to use all information collected prior to the revocation of subject authorization. For subjects that have revoked authorization to collect or use PHI, attempts should be made to obtain permission to collect

at least vital status (i.e. that the subject is alive) at the end of their scheduled study period. We will exercise the following practices to maintain confidentiality of data and protecting against unauthorized disclosure:

- not downloading identifying information from REDCap except subject ID number (i.e., keep any identifying information separately from any research data)
- locking up research files while they are unsupervised
- using screensavers
- shredding excess copies of paper documents
- protections for codes that link patients to their data
- electronic and physical security of data storage devices and networks
- security measures to protect storage and transmission of electronic data

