11. DATA ANALYSIS AND MONITORING

11.1. Sample Size Determination

The pilot study^{2,3} showed that mastoid oscillation treatment was highly efficacious. Of 66 subjects that were treated, 22 (33.3%) achieved complete control, 30 (45.4%) achieved substantial control, 11 (16.7%) achieved limited control and three (4.5%) had insignificant control. A control group (N=30) with delayed start of treatment had just 2 subjects with improvement of symptoms (complete or substantial) during the wait period (6.6%).

For our sample size projection, we assume that the Mastoid Oscillation arm will have a 75% rate of achieving substantial or complete control, and 12% for the placebo group. With 15 subjects in each group, using Fisher's Exact test, the design has 95% statistical power with alpha of 0.012.

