11.2. Planned Statistical Analysis

At the completion of the last study subject, the blinding will be broken and the aggregate results of the treatment and control arm will be compared.

The primary outcome measure is the change in monthly vertigo episodes. Per the AAO guidelines⁴, this has a numeric value of $X/Y \times 100$, where X is the average number of definitive spells per month after therapy, and Y is that rate prior to therapy. Categories A-F are designated, and the Chi-square/Fisher's Exact test will be used to compare the treatment and placebo groups.

[figure not shown]
Numeric Value	Class	Description
0	A	Complete control
1 to 40	B	Substantial control
41 to 80	C	Limited Control
81 to 120	D	Insignificant Control
> 120	E	Worsening of symptoms
	F	Secondary treatment initiated due to disability from vertigo

Secondary outcome measures are the average hearing threshold and word recognition score, which will be compared by repeated-measures ANOVA. Another secondary outcome measure is the patient Meniere's functional level before and after treatment (Appendix 2).

[figure not shown]

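### Section 6 ends follow-up as well as device sessions for subjects the investigator withdraws, so obtainable day-90 outcomes are not collected, and 11.2 does not say how these subjects are classed

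*Combined protocol and SAP*

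**What the plan says.** Section 6 gives three grounds on which the investigator removes a subject. The first is missed visits: "Subjects will be withdrawn from the research without their consent by the investigator if they are non-compliant (miss scheduled study visits". The others are a judgement that withdrawal is better for the subject, and bilateral disease that appears during the study. The removal is from the research as a whole. The section does not distinguish stopping device sessions from stopping assessments. It adds "There are no additional study activities requiring completion prior to subject withdrawal from the study" and "Subjects withdrawn from the study will not be replaced".

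Under section 5, the longer-term outcome is taken at the final visit, three months after enrolment (day 90 in the schedule), when the frequency and severity of "attacks will be recorded and compared to pretreatment patterns". Interim information also exists. Under section 5.2, subjects are asked at each visit after the first "if they have had vertigo episodes since the last visit, and if so how frequent and of what duration", and visit 5 (day 35) looks at short-term results.

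Section 11.2 says that after unblinding "the aggregate results of the treatment and control arm will be compared". Classes A to E come from the ratio of post-treatment to pretreatment monthly spells, and class F covers secondary treatment. The section names no analysis set, no rule for missing classes and no sensitivity analysis.

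Section 9 has the only provision for contact after leaving. It applies to subjects who revoke authorisation for their health information, and it seeks "at least vital status (i.e. that the subject is alive) at the end of their scheduled study period".

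**The concern.** Missed visits, new bilateral disease and the investigator's judgement all arise after randomisation, and any of them may be related to symptoms. A subject who skips a weekly session, or whose other ear becomes affected, can usually still say how many vertigo attacks occurred. Section 4.1 recruits from the investigator's own practice, and section 5 notes that subjects are typically established patients there, so many would be reachable by telephone or through the chart. Followed as written, section 6 forgoes those outcomes.

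The stake is the comparison of the arms as randomised. If withdrawn subjects are left out, the arms compared are those who stayed. If their partial counts are used, the observation period differs between subjects. Section 11.2 chooses neither, so the choice could fall after the blind is broken. With 15 per arm, a few subjects can change the result. In a constructed case, 8/15 versus 2/15 responders gives a two-sided Fisher p of 0.050. Leaving out three active-arm non-responders gives 8/12 versus 2/15 and p = 0.007.

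**Working it through.** **Inputs from the documents.** 15 per arm (sections 3.1 and 11.1); "75% rate of achieving substantial or complete control, and 12% for the placebo group", Fisher's exact test, alpha 0.012 and power 95% (section 11.1); visits 2 to 5 on days 7, 14, 21 and 35 and visit 6 on day 90 (schedule in section 5).

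**Assumptions, not in the documents.** The rates of missed visits, independence of misses, all selective-loss rates, a two-sided test, and an analysis of classes A/B against the rest. That split is the one used for the sample size; 11.2 lists A to F.

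**Step 1: the plan's own figure.** Exact enumeration of all binomial outcomes at 15 per arm, 75% versus 12%, gives two-sided Fisher power of 82.8% at 0.012 and 92.0% at 0.05. The stated 95% at 0.012 is not reproduced. That is a separate issue. The baselines below are 83% and 92%.

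**Step 2: how many subjects the missed-visit rule could remove.** Visit 6 is left out, because a subject who misses it has no day-90 assessment whatever section 6 says. With probability q of missing each of the four visits:

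- withdrawn if one miss is enough: 1 − (1 − q)^4
- withdrawn if two are needed: 1 − (1 − q)^4 − 4q(1 − q)^3

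For q = 0.02: 1 − 0.9224 = 7.8%, and 1 − 0.9224 − 0.0753 = 0.2%. For q = 0.05: 1 − 0.8145 = 18.5%, and 1 − 0.8145 − 0.1715 = 1.4%. The text does not say how many misses count.

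**Step 3: power if those subjects are dropped at random** (numbers remaining are binomial in each arm).

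| Rule and q | Withdrawn | Per arm (× 15) | Power at 0.05 | Power at 0.012 |
|---|---|---|---|---|
| No loss | 0% | 0 | 92% | 83% |
| One miss, 2% | 7.8% | 1.2 | 92% | 79% |
| One miss, 5% | 18.5% | 2.8 | 89% | 70% |
| Two misses, 2% | 0.2% | 0.04 | 92% | 83% |
| Two misses, 5% | 1.4% | 0.2 | 92% | 83% |

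**Step 4: type I error with no true effect, non-responders lost from one arm only.** Expected subjects lost = 15 × (1 − response rate) × fraction lost.

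| Response rate, both arms | Fraction of failures lost | Subjects lost | Rejection at 0.05 | Rejection at 0.012 |
|---|---|---|---|---|
| 12% | none | 0 | 0.8% | 0.03% |
| 12% | 25% | 3.3 | 2.0% | 0.3% |
| 12% | 50% | 6.6 | 5.1% | 1.2% |
| 30% | none | 0 | 1.7% | 0.3% |
| 30% | 25% | 2.6 | 3.7% | 0.9% |
| 30% | 50% | 5.25 | 9.0% | 2.7% |

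Equal loss in both arms, at 25% or 50%, stays below 3% at 0.05 for either response rate. Fisher's test is conservative at this size, which absorbs moderate selective loss.

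**Step 5: direction.** At 75% versus 12%, losing half of the placebo failures (15 × 0.88 × 0.5 = 6.6 subjects) raises the expected placebo rate to 0.12/(0.12 + 0.44) = 21% and lowers power at 0.05 from 92% to 65%. Losing half of the active failures (15 × 0.25 × 0.5 = 1.9 subjects) raises the expected active rate to 0.75/(0.75 + 0.125) = 86% and raises power to 99%. The distortion can run either way.

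**The case against.** The strongest reply is that the plan does not say withdrawn subjects leave the analysis. Section 11.2 fixes no post-therapy window, so a subject with any post-treatment count could be given a ratio and a class. This stands. A reader might infer that withdrawn subjects' data are discarded, but no sentence says so. What is not collected is the later follow-up, including day 90. What is unstated is whether the earlier counts are used. Likewise, the sentence that nothing need be completed before withdrawal concerns exit procedures. It does not forbid later contact, although none is planned.

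Second, a reader might infer that the rule favours the device or inflates false positives. The documents do not support that. The study team is blinded (sections 5 and 7.2), and no withdrawal rates or reasons by arm are given. Nothing links missed visits or bilateral disease to arm or response. The cases in which half of one arm's failures are lost and none in the other are extreme, and at the protocol's 12% rate they only bring the error to about its nominal level. Blinding of staff does not, however, stop a subject's attendance from depending on symptoms.

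Third, section 3.1 allows up to 40 to be enrolled to accrue 15 plus 15, which may cushion the numbers. The purpose of the margin is not stated, section 6 bars replacement, and extra subjects would not undo selection.

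Fourth, bilateral disease is an exclusion criterion, so one may ask whether such subjects still answer the question. Exclusion at entry does not justify removal for something that develops after randomisation; as-randomised analysis keeps them in.

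Finally, some subjects who miss visits will be unreachable, so not every outcome can be recovered.

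**Conclusion.** The point holds as one of design and specification. Section 6 as written stops follow-up for subjects whose day-90 outcome could often be obtained, section 9 does not restore it, and 11.2 leaves their classification open. The size and direction of any bias cannot be determined from the documents.

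Under the assumed miss rates, the cost in power at 0.012 is 4 to 13 percentage points if a single miss triggers withdrawal and the losses are random. At 0.05 it is at most about 3 points. If two misses are required, it is negligible. A clear excess of type I error appears only with loss of about half of one arm's failures, none in the other, and a response rate near 30%. All of this rests on the assumed A/B split and a two-sided test. The change is worth making because it is cheap and protects the randomised comparison, not because serious bias has been shown.

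**What to change.** In section 6, separate stopping device sessions from ending follow-up. Unless the subject withdraws consent, seek the day-90 vertigo count, the functional level and any secondary treatment for every randomised subject, by telephone or chart where a visit is not possible.

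In section 11.2, state that all randomised subjects are analysed in their assigned arm, including those who became non-compliant or developed bilateral disease. State how counts recorded before withdrawal are used. For classes still missing, report a best-/worst-case sensitivity analysis. Fix all of this before unblinding. Class F already covers secondary treatment and needs no new rule.

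Who stops device treatment, and when, is unchanged. The cost is revised wording in two sections, a few telephone or chart contacts, and slightly more analysis.
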